8.3.3 Investigator reporting: *Notifying UNC if affiliate site*

N/A

8.3.4 Sponsor reporting: Notifying the FDA

The study sponsor is required to report certain study events in an expedited fashion to the FDA. These written notifications of adverse events are referred to as IND safety reports. The following describes the safety reporting requirements by timeline for reporting and associated type of event:

- ***Within 7 calendar days***

Any study event that is:

- associated with the use of the study drug
- unexpected,
- fatal or life-threatening, and

- ***Within 15 calendar days***

Any study event that is:

- associated with the use of the study drug,
- unexpected, and
- serious, but not fatal or life-threatening
 - or-
- a previous adverse event that was not initially deemed reportable but is later found to fit the criteria for reporting (reporting within 15 calendar days from when event was deemed reportable).

Any finding from tests in laboratory animals that:

- suggest a significant risk for human subjects including reports of mutagenicity, teratogenicity, or carcinogenicity.

Additional reporting requirements

Sponsors are also required to identify in IND safety reports all previous reports concerning similar adverse events and to analyze the significance of the current event in light of the previous reports.

Reporting Process

Adverse events may be submitted on FDA Form 3500A or in a narrative format. If supplied as in a narrative format, the minimum information to be supplied is noted above at the beginning of section 8.3. All adverse events will be reported to the FDA.

8.3.5 Sponsor reporting: Notifying participating investigators

It is the responsibility of the study sponsor to notify all participating investigators, in a written IND safety report, of any adverse event associated with the use of the drug that is both serious and unexpected, as well as any finding from tests in laboratory animals that suggest a significant risk for human subjects. Additionally, sponsors are also required to identify in IND safety reports all previous reports concerning similar adverse events and to analyze the significance of the current event in light of the previous reports.

8.4 Unblinding Procedures

In the event of a SAE or discontinuation from the study, subjects will be unblinded.

8.5 Stopping Rules

The Data and Safety Monitoring plan contains rules for discontinuing individual participant and rules for stopping the entire study. In the event of three grade 3 or higher adverse events (i.e. a life threatening adverse event that may require hospitalization) possibly or definitely associated with the study intervention, the study will be suspended and the study's Data and Safety Monitoring Board will be notified.

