4.4 Early Withdrawal of Subjects

4.4.1 When and How to Withdraw Subjects

Participants with significant clinical or laboratory abnormalities will be discontinued from the study prior to GnRH agonist administration.

As the population being studied in this protocol may be at high risk to develop subsequent depressions and as gonadal steroids have been implicated in the etiology of postpartum depression, some depressive reactions, including suicidal ideation, may occur during this protocol. However, based on

experience with Lupron and estradiol/progesterone addback in women with menstrually-related mood disorders, we would expect mood symptoms to be of mild to moderate severity.

Adverse mood symptoms, including suicidal ideation, will be monitored on a bi-weekly basis by administering the Inventory of Depression and Anxiety Symptoms (IDAS-II). The IDAS-II will be [REDACTED] scored during the study visit (before the patient leaves the hospital). IDAS-II Suicidality Scale scores [REDACTED] of > 8 are observed at any period in the protocol or any subject with suicidal ideation, or anyone with concerns about their ability to continue in the study, will be considered to have severe mood symptoms and be discontinued from the protocol.

In the event of the occurrence of severe mood symptoms, either the protocol will be terminated, or if symptoms occur during the withdrawal phase, hormone replacement will be re-instituted. Should this step prove to be unsuccessful, conventional medication will be prescribed as needed. Further, although we do not anticipate severe adverse reactions, participants may be hospitalized in a UNC Neurosciences Hospital Inpatient Psychiatry Clinic if symptoms are otherwise unmanageable.

Any patient experiencing clinically significant side effects such as nausea, hypertension, vomiting or extreme fluid retention from the medication will have the dose titrated to achieve relief of the symptoms. If adequate relief cannot be achieved in this manner, drug treatment will be discontinued. Similarly, if menopausal-like symptoms occurring secondary to GnRH agonist treatment are intolerable, drug treatment will be discontinued. Additionally, study medication will be terminated in subjects that experience any grade 3 or higher adverse events that limit their activities of daily living, that cannot be otherwise addressed by modifying a medication dose.

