In the event of three grade 3 or higher adverse events (i.e. a life threatening adverse event that may require hospitalization) possibly or definitely associated with the study intervention, the study will be suspended and the study's Data and Safety Monitoring Board will be notified.

The determination of when and how to withdrawal subjects will be overseen by the study's Data and Safety Monitoring Board and will be reported to the UNC Biomedical IRB.

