8.1 Definitions

Unanticipated Problems Involving Risk to Subjects or Others

Any incident, experience, or outcome that meets all of the following criteria:

- Unexpected in nature, severity, or frequency (i.e. not described in study-related documents such as the IRB-approved protocol or consent form, the investigators brochure, etc.)
- Related or possibly related to participation in the research (i.e. possibly related means there is a reasonable possibility that the incident experience, or outcome may have been caused by the procedures involved in the research,
- Serious (as defined below) “Serious” is different than “severe” as reported in the CTC criteria that applies a grade to the AE.

Adverse Event

An **adverse event** (AE) is any symptom, sign, illness or experience that develops or worsens in severity during the course of the study. Intercurrent illnesses or injuries should be regarded as adverse events. Abnormal results of diagnostic procedures are considered to be adverse events if the abnormality:

- results in study withdrawal
- is associated with a serious adverse event
- is associated with clinical signs or symptoms
- leads to additional treatment or to further diagnostic tests
- is considered by the investigator to be of clinical significance

Serious Adverse Event

Adverse events are classified as serious or non-serious. A **serious adverse event** is any AE that is:

- fatal
- life-threatening
- requires or prolongs hospital stay
- results in persistent or significant disability or incapacity
- a congenital anomaly or birth defect
- an important medical event

Important medical events are those that may not be immediately life threatening, but are clearly of major clinical significance. They may jeopardize the subject, and may require intervention to prevent one of the other serious outcomes noted above. For example, drug overdose or abuse, a seizure that did not result in in-patient hospitalization, or intensive treatment of bronchospasm in an emergency department would typically be considered serious.

All adverse events that do not meet any of the criteria for serious should be regarded as **non-serious adverse events**.

Adverse Event Reporting Period

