5. Every event will be reported to the principal investigator and [name] by the designated research associates and will be documented. An adverse event report will be generated for each even and will include a description of the event, when and how it was reported, and any official chart records or documentation to corroborate the event.
6. The adverse event report will also include the severity attribution of the adverse event using the Common Toxicity Criteria (CTC) scale: 0 = no adverse event or within normal limits; 1 = mild AE, not requiring treatment; 2 = moderate AE, resolved with treatment; 3 = severe AE, resulted in inability to carry on normal activities and required professional medical attention; 4 = life threatening or disabling AE; 5 = fatal AE.
7. The adverse event report will also include a determination of attribution according to the following scale: 0 = definitely not related; 1 = probably not related; 2 = possibly related; 3 = probably related; 4 = definitely related.

III. Safety Review Plan and Monitoring

Oversight of participant safety includes a review of adverse events as well as study progress, data integrity, and study outcomes.

A. Justification of sample size

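### The study-suspension trigger says grade 3 but defines it as life threatening, and the safety monitoring plan omits the rule that suicidal ideation means discontinuation

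*Combined protocol and SAP*

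**What the plan says.** **Suspending the study.** Section 8.5 suspends the study and notifies the DSMB after "three grade 3 or higher adverse events (i.e. a life threatening adverse event that may require hospitalization) possibly or definitely associated" with the intervention. Section 4.4.1 carries the same trigger and the same parenthesis, beginning "In the event of three grade 3 or higher adverse events".

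**Grading.** Section 8.1 separates serious from severe and describes severity "as reported in the CTC criteria that applies a grade to the AE". Appendix C, II.B item 6, sets out that scale: "3 = severe AE, resulted in inability to carry on normal activities and required professional medical attention; 4 = life threatening or disabling AE", with grade 5 fatal. Item 7 gives five levels of attribution, the top three being possibly, probably and definitely related.

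**Stopping for one woman.** Section 4.4.1 warns that "some depressive reactions, including suicidal ideation, may occur during this protocol". It then names three grounds for discontinuation. One is an IDAS-II suicidality score above 8 (that sentence is partly blacked out). The other two follow: "any subject with suicidal ideation, or anyone with concerns about their ability to continue in the study, will be considered to have severe mood symptoms". Section 6 also discontinues for severe depressive symptoms and gives suicidal ideation as its example.

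**The safety monitoring plan.** Section 8.5 says that this plan contains the individual discontinuation rules. Those are in Appendix C III.C. There, suicidal thoughts or severe mood symptoms lead to a phone call from the principal investigator. A woman who voices doubts about carrying on is deemed severe and discontinued, and severe mood symptoms end the protocol.

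**The concern.** Both rules are safety thresholds that staff must be able to apply the same way every time. The first gives a number and a definition that point to different grades, so two careful readers could disagree on whether the study must be suspended. The second is complete in the body of the protocol but loses its suicidality criteria in the plan that Section 8.5 cites for individual discontinuation. The protocol itself foresees ideation, so this is not a remote case. At stake is whether suspension and discontinuation happen when intended. Nothing in the estimation or testing of the hypotheses depends on it.

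**Working it through.** The documents state no figure to reproduce. The check sets the texts side by side.

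**A. Suspension trigger**

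1. *Which scale applies?* Section 8.1 ties severity grades to the CTC criteria, and Appendix C II.B item 6 is where the document sets out the CTC scale. Grade 3 there is severe; life threatening first appears at grade 4.
2. *Is the parenthesis only an example?* No. It is introduced by i.e., which restates a term.
3. *Apply both readings to exactly three related events, with the trigger at 3.* Grade 4 events are taken as life threatening.

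| Grades | Count by the number | Count by the definition |
|---|---|---|
| 3, 3, 3 | 3 (suspend) | 0 (continue) |
| 3, 3, 4 | 3 (suspend) | 1 (continue) |
| 3, 4, 4 | 3 (suspend) | 2 (continue) |
| 4, 4, 4 | 3 (suspend) | 3 (suspend) |

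The readings differ whenever at least one of the three is a grade 3 event. A grade 4 event that is disabling but not life threatening would also fail the definition. The table only works through the two definitions; it is not an estimate of how often they would diverge.

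4. *Which half is the slip?* Elsewhere Section 4.4.1 says "study medication will be terminated in subjects that experience any grade 3 or higher adverse events that limit their activities of daily living", unless a dose change can deal with them. That is grade 3 in its Appendix C sense, tied to daily function and not to threat to life. It suggests that the number is intended and the parenthesis is wrong, but does not prove it.
5. *Does another rule settle it?* Section 8.5 says the safety monitoring plan also holds rules for stopping the whole study. The Appendix C text available to me has a stopping section for individual subjects only. Part of the public file is missing, so I do not claim that no such rule exists.
6. *Attribution.* The trigger names possibly and definitely associated events and skips the level between them. Read literally, a possibly related event counts and a probably related one does not. That cannot be intended.

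**B. Individual rule**

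| Finding | Section 4.4.1 | Section 6 | Appendix C III.C |
|---|---|---|---|
| Suicidality score criterion | severe, discontinued | not mentioned | not mentioned |
| Suicidal ideation | severe, discontinued | severe, discontinued | phone call; not classed as severe |
| Doubts about continuing | severe, discontinued | not mentioned | severe, discontinued |
| Severe mood symptoms | see the three rows above | discontinued (severe depressive symptoms) | phone call; protocol terminated |

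III.C keeps the consequence of severe mood symptoms but not the statement that ideation or the score criterion puts a woman in that class. It also lists suicidal thoughts and severe mood symptoms as alternatives, which invites the view that they are different things.

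**The case against.** The best reply is that this is drafting, and that a sensible team would act safely.

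On suspension, the number appears identically in two places, grade 3 is defined once, and applying the number gives the more protective result. There are also backstops. Section 4.4.1 stops medication for limiting grade 3 events. Section 8.3.1 sends serious adverse events to the sponsor and DSMB within 24 hours. The principal investigator reviews events as they occur, and the DSMB can meet in emergency. Section 1.4 reports no serious adverse events in earlier hormone-challenge studies. All of this is true and lowers the practical risk. None of it says which grade suspends the study, and a grade 3 event is not necessarily a serious adverse event.

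On the individual rule, the body of the protocol states it twice, and Appendix C I.B promises adherence to the approved protocol. Appendix C II.A sends a woman to the Emergency Department when suicidal thoughts come with intent, a plan and the means. The promise is general, and the Emergency Department step does not cover ideation alone. Neither supplies the missing definition.

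A reader might infer more than the documents support:

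- *That III.C contradicts 4.4.1 and keeps women with ideation in the study.* It does not. The phone call applies equally to severe mood symptoms, for which III.C ends the protocol, so a call does not imply retention. III.C is incomplete, not contrary.
- *That 4.4.1 is inconsistent about the withdrawal phase*, because after discontinuation it says "either the protocol will be terminated, or if symptoms occur during the withdrawal phase, hormone replacement will be re-instituted". Followed by conventional medication if that fails, this reads naturally as a rescue sequence.
- *That Section 10.1 hands clinical discontinuation to Appendix C.* That section concerns monitoring and quality-assurance access. Only Section 8.5 makes the relevant reference.

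**Conclusion.** The point holds as an internal inconsistency in two safety rules. The suspension trigger contradicts the document's own grading scale: three related, severe, non-life-threatening events suspend the study by the number and not by the definition. Appendix C III.C leaves out the rule in Sections 4.4.1 and 6 that suicidal ideation means discontinuation, along with the score criterion in 4.4.1.

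The first conclusion assumes that the Appendix C scale governs the grades in 8.5, which Section 8.1 supports. The second needs no assumption beyond the text. It is tempting to attach a probability of suspension to each reading, but the documents give no rates of related grade 3 or grade 4 events, so any such figure would rest wholly on assumed rates. The number of women affected by the omission in III.C cannot be estimated either. There is no effect on the analysis. The correction is warranted because the rules protect participants and cost little to put right.

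**What to change.** 1. In Sections 4.4.1 and 8.5, delete the life-threatening parenthesis or replace it with the Appendix C wording for grade 3. Write possibly, probably or definitely related, to match the attribution scale. The investigators and DSMB should confirm that grade 3 is the intended threshold.
2. In Appendix C III.C, state that suicidal ideation, or the suicidality score criterion of 4.4.1, counts as severe mood symptoms and means discontinuation. Keep the principal investigator's phone call and the Emergency Department step as additional actions.

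The cost is amendment wording in three places, with no new visits, procedures or participants. The downside is that a suspension becomes more likely, since severe events that are not life threatening, and probably related events, would then plainly count. The documents do not allow the size of that increase to be estimated.

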8.6 Medical Monitoring

The principal investigator will oversee the safety of the study at his/her site. This safety monitoring will include careful assessment and appropriate reporting of adverse events as noted above, as well as the construction and implementation of a site data and safety-monitoring plan. Medical monitoring will include a regular assessment of the number and type of serious adverse events.

8.6.1 Independent Data and Safety Monitoring Board

The Data Safety Monitoring Board (DSMB) will act in an advisory capacity to the University of North Carolina at Chapel Hill (UNC-CH) Institutional Review Board (IRB) to monitor patient safety and evaluate the efficacy of the intervention.

DSMB RESPONSIBILITIES

The initial responsibility of the DSMB will be to approve the initiation of this clinical trial. After this approval and at periodic intervals, following the enrollment and protocol start of 10 subjects or at 6 months intervals during the course of the trial, the DSMB responsibilities are to:

- review plans for data safety and monitoring;
- evaluate the progress of the trial, including safety events, accrual and retention, and other factors that can affect study outcome;
- make recommendations to the PI concerning continuation, termination, or other modifications of the trial based on the reported beneficial or adverse effects of the treatment under study;
- if appropriate, review interim analysis of efficacy in accordance with stopping rules which are clearly defined in advance of data analysis and have the approval of the DSMB;
- assist the UNC-CH IRB by commenting on any problems with enrollment, and sample size.

MEMBERSHIP

The DSMB will consist of at least three members, and the presence of all three members will be required to constitute a quorum. The members, recommended by NCTraCS, will include an obstetrician-gynecologist, a biostatistician, and a psychiatrist (not affiliated with the UNC Department of Psychiatry) and will be subject to approval by the UNC-CH IRB. Membership will consist of persons completely independent of the investigators who have no financial, scientific, or other conflict of interest with the trial. Collaborators or associates of [name] are not eligible to serve on the DSMB. Written documentation attesting to absence of conflict of interest is required. The DSMB includes experts in or representatives of the fields of:

- a psychiatrist with relevant clinical experience,
- an obstetrician-gynecologist with relevant clinical experience;
- clinical trial methodology, and
- biostatistics.

The DSMB chairperson will be responsible for overseeing the meetings, developing the agenda in consultation with [name] and the UNC-CH IRB, as required. The chair is the contact person for the DSMB

A Safety Officer will be identified by [name] at the first meeting. This person will be the contact person for severe adverse event reporting. The Safety Officer will notify the DSMB and UNC-CH IRB of serious adverse events within 24 hours. Procedures for notifying the Chair of the DSMB and UNC-CH IRB will be determined at the first meeting.

BOARD PROCESS

The first meeting will take place face-to-face to discuss the protocol, any modifications of the trial, and to establish guidelines to monitor the study. The DSMB Chairperson and [name] will prepare the agenda to address the review of the manual of operating procedures, modification of the study design, initiation of the trial, identification of a safety officer, reporting of adverse events, stopping rules, interim analysis plan, etc.

Meetings of the DSMB will be held two times a year at the call of the Chairperson. Meetings shall be closed to the public because discussions may address confidential patient data. Meetings are attended, when appropriate, by the principal investigator and members of her staff. Meetings may be convened as conference calls as well as in person, although the initial meeting and meetings to discuss interim analysis will be face-to-face. An emergency meeting of the DSMB may be called at any time by the Chairperson or by the UNC-CH IRB should questions of patient safety arise.

MEETING FORMAT

An appropriate format for DSMB meetings consists of an open and closed session. The open sessions may be attended by the principal investigator(s), institution staff and UNC-CH IRB staff, and should always include the study biostatistician. Issues discussed at open sessions will include the conduct and progress of the study, including patient accrual, compliance with protocol, and problems encountered. Patient-specific data and treatment group data may not be presented in the open session.

The closed session will be attended only by voting DSMB members. The DSMB may request others to attend part or all of the closed sessions (e.g., the study statistician, UNC-CH IRB staff). All safety and efficacy data are and must be presented at this session. The discussion at the closed session is completely confidential.

The DSMB will conduct an interim review following the enrollment of 10 subjects, or at 6 month intervals, whichever is soonest.

Should the DSMB decide to issue a termination recommendation, full vote of the DSMB will be required. In the event of a split vote, majority vote will rule, and a minority report should be appended.

REPORTS

- 1. Interim Reports:** Interim reports are generally prepared by the study statistician and distributed to the DSMB at least 10 days prior to a scheduled meeting. These interim reports are numbered and provided in sealed envelopes within an express mailing package or by secure email as the DSMB prefers. The contents of the report are determined by the DSMB. Additions and other modifications to these reports may be directed by the DSMB on a one-time or continuing basis. Interim data reports generally consist of two parts:

Part 1 (Open Session Report) provides information on study aspects such as accrual, baseline characteristics, and other general information on study status.

Part 2 (Closed Session Report) may contain data on study outcomes, including safety data, and depending on the study, perhaps efficacy data. The Closed Session Report is considered confidential and should be destroyed at the conclusion of the meeting. Data files to be used for interim analyses should have undergone established editing procedures to the extent possible. Interim analyses of the efficacy data are performed only if they are specified and approved in advance and criteria for possible stopping is clearly defined.

- 1. Reports from the DSMB:** A formal report containing recommendations for continuation or modifications of the study prepared by the DSMB Chairperson will be sent to the full DSMB within four weeks of the meeting. Once approved by the DSMB, the formal DSMB recommendation will be forwarded to [name]. It is [name] responsibility to distribute the formal DSMB recommendation report to all co-investigators and to assure that copies are submitted to all the IRBs associated with the study.

As previously stated, the formal DSMB report should conclude with a recommendation to continue or to terminate the study. This recommendation should be made by a formal majority vote. A termination recommendation may be made by the DSMB at any time by a majority vote. The DSMB Chairperson is responsible for notifying [name] of a decision to terminate the study. In the event of a split vote in favor of continuation, a minority report should be contained within the regular DSMB report. The report should not include unblinded data, discussion of the unblinded data, etc.

Mailings to the DSMB: On a scheduled basis (as agreed upon by the DSMB) blinded safety data should be communicated to all DSMB members or to the designated safety officer (to be determined at the first meeting). Any concerns noted should be brought to the attention of the DSMB Chairperson.

Access to Interim Data: Access to the accumulating endpoint data should be limited to as small a group as possible. Limiting the access to interim data to the DSMB members relieves the investigator of the burden of deciding whether it is ethical to continue to enroll patients and helps protect the study from bias in patient entry and/or evaluation.

CONFIDENTIALITY

All materials, discussions and proceedings of the DSMB are completely confidential. Members and other participants in DSMB meetings are expected to maintain confidentiality.

9 Data Handling and Record Keeping

